# 8.4.2 SERIOUS ADVERSE EVENT REPORTING

Any clinical adverse event or abnormal laboratory test value that meets the definition of serious noted below and occurs in a patient during the course of the study, irrespective of the treatment received by the patient, must be reported within 24 hours of the investigator becoming aware of the occurrence. Serious adverse event definition and reporting requirements will be in accordance with the International Conference of Harmonisation (ICH) Guideline for Clinical Safety Data Managements.

# Definitions and Standards for Expedited Reporting, Topic E2A:

An SAE is defined as any untoward medical occurrence that at any dose:

1. Results in death

2. Is immediately life-threatening (i.e., in the opinion of the investigator, the AE places the patient at immediate risk of death; it does not include a reaction that, had it occurred in a more severe form, might have caused death)

- 3. Requires inpatient hospitalization or results in prolongation of an existing hospitalization
- 4. Results in persistent or significant disability or incapacity
- 5. Is a congenital anomaly or birth defect

6. Is an important medical event that may not be immediately life-threatening, result in death, or require hospitalization, but may be considered an SAE when, based upon appropriate medical judgment, it jeopardizes the patient or may require medical or surgical intervention to prevent one of the outcomes listed above.

Any SAE, whether or not considered to be related to study treatment, will be reported within 24 hours of the investigator becoming aware of the event. It will be recorded on both the SAE form and the CRF AE page. Additional SAE information including medications or other therapeutic measures

used to treat the event, action taken with the study drug due to the event, and the outcome / resolution of the event will be recorded on the SAE form. Forms for reporting SAEs will be provided to the study sites.

Conversely, some hospitalizations, particularly those that are the result of elective or previously scheduled surgery for preexisting conditions, which have not worsened after initiation of treatment, will not be classified as SAEs. For example, an admission for a drainage of obstructed bile duct would not be classified as an SAE. Pre-specified study hospitalizations for observation are not considered SAEs. All overdoses, whether or not resulting in an AE, require reporting within 24 hours.

All Grade 3 and greater AEs and SAEs that occur after the first treatment with RT and through 4 weeks of treatment will require reporting by the investigational site. SAEs that meet the criteria for expedited reporting to the FDA will be reported in accordance with US regulations governing safety reporting (Title 21 of the Code of Federal Regulations [CFR] 312.32 and 312.33). Reporting of SAEs by the investigator to his or her Institutional Review Board (IRB) will be done in accordance with the standard operating procedures and policies of the IRB. Adequate documentation must be maintained showing that the IRB was properly notified.

In case of an SAE, the investigator will electronically report to the University of South Florida Institutional Review Board via website http://www.research.usf.edu/cs/.

# 8.4.3 UNANTICIPATED PROBLEM REPORTING

Incidents or events that meet the OHRP criteria for UPs require the creation and completion of an UP report form. It is the site investigator's responsibility to report UPs to their IRB and to the DCC/study sponsor. The UP report will include the following information:

- Protocol identifying information: protocol title and number, PI's name, and the IRB project number;
- A detailed description of the event, incident, experience, or outcome;
- An explanation of the basis for determining that the event, incident, experience, or outcome represents an UP;
- A description of any changes to the protocol or other corrective actions that have been taken or are proposed in response to the UP.

To satisfy the requirement for prompt reporting, UPs will be reported using the following timeline:

- UPs that are SAEs will be reported to the IRB and to the DCC/study sponsor within 1 day of the investigator becoming aware of the event.
- Any other UP will be reported to the IRB and to the DCC/study sponsor within 7 days of the investigator becoming aware of the problem.

#### 8.5 STUDY HALTING RULES

Not Applicable

#### 8.6 SAFETY OVERSIGHT

The Protocol Monitoring Committee (PMC) monitors its assigned ongoing research protocols for adverse event reporting, data and safety monitoring, and internal audit findings. The PMC,

upon review of any agenda item, may approve the study for continuation, require revisions, or suspend or close a protocol. This study will be reviewed by the PMC for data and safety monitoring. The principal investigator will enter into Oncore all adverse events and deviations as they occur for review by the PMC.

The Principal Investigator is ultimately responsible for every aspect of the design, conduct, and actions of all members of the research team. This includes final analysis of the protocol.

# 9 CLINICAL MONITORING

This study will be monitored internally by Moffitt Cancer Center using the OnCore reporting system. Data will be captured in OnCore, Moffitt's electronic Clinical Trials Database. For each participant enrolled, the electronic CRF must be completed by the assigned data manager or other authorized study staff. Any paper forms should be typed or filled out indelible ink and must be legible. Errors should be crossed out but not obliterated, the correction inserted, and the change initialed and dated by the investigator or his/her authorized delegate. This also applies to records for those patients who fail to complete the study. If a patient stops dosing or terminates from the study, the dates and reasons must be noted on the CRF. If a patient terminates from the study because of a DLT, thorough efforts should be made to clearly document the outcome. The Case Report Forms will be reviewed by Moffitt's Internal Monitors periodically throughout the conduct of the trial. The monitoring will include source data verification, utilizing research patients' medical records. The investigator should ensure the accuracy, completeness, legibility, and timeliness of the data reported to the protocol monitoring committee.

Each Scientific Review Committee conducts a formal internal peer review of all clinical protocols and general scientific oversight of interventional clinical research. Protocols are reviewed for scientific merit, adequate study design, safety, availability of targeted study population, and feasibility of timely completion of all proposed research projects to be conducted by its assigned programs at the Cancer Center. Each SRC is responsible for evaluating the risk/benefit assessment and corresponding data and safety monitoring plan as part of the scientific review and approval process.

No modifications will be made to the protocol without the agreement of the investigators. Changes that significantly affect the safety of the patients, the scope of the investigation, or the scientific quality of the study will require Scientific Review Committee and Institutional Review Board approval before implementation, except where the modification is necessary to eliminate apparent immediate hazard to human subjects. Any departures from the protocol must be fully documented in the case report form and the source documentation.

# **10 STATISTICAL CONSIDERATIONS**

# **10.1 STATISTICAL AND ANALYTICAL PLANS**

Demographic information such as age and race will be tabulated. Descriptive statistics, including means, standard deviations, and ranges for continuous parameters, as well as percents and frequencies for categorical parameters, will be presented.

The effectiveness of PSI to select fractionation schema will be assessed by percent response at the 4th week of treatment. One-sided 95% confidence interval for the percent response at the 4th week of treatment will be also reported. A proportion difference test will be performed to test a difference of complete response rate from a target of 49%.

As for secondary endpoints, response will be correlation with pre-treatment and during treatment radiomics features on PET/CT/MRI using two sample t-tests and univariate/multivariate logistic regression analysis as appropriate. Correlation of response and outcomes to the mathematical models of tumor growth and death dynamics pre-treatment and during treatment will be performed using logistic regression analysis.

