Additionally, recent review of Moffitt Cancer Center internal data suggests that patients with greater than 5 positive lymph nodes are at a higher risk of regional failure, with locoregional control at 3 years of 94.9% for 1-5 lymph nodes vs 80.1% for > 5 lymph nodes (p = 0.001). By restricting patients to T1-2 N0-1 with 5 or less lymph nodes and a smoking history of 10 pack years or less, 3-year locoregional control of patients treated with radiation alone at Moffitt Cancer Center was 94.7% (n=81) compared to 95.9% with concurrent radiotherapy and systemic therapy (n=98) (personal communication [name]).

In a retrospective analysis of 44 patients, decrease in nodal size of  $\geq$  40% was associated with a locoregional control (LRC) of 100% at 2 years, compared with 78% for a decrease of < 40%. Retrospective review of a Moffitt cohort (n=49) suggests that a cut point of 32% reduction resulted in 100% LRC and DFS (Figure 2A&B). Of note, half of these patients were treated with radiation alone.

In the mathematical modeling of radiation treatment response, there is a suggestion of a more robust treatment response by hyperfractionation when the PSI is > 0.75 (Figure 3).

[figure not shown]

Figure 3: Model of tumor response at 4 weeks by initial pretreatment PSI.

We therefore hypothesize that by personalizing the fractionation, we will increase the number of patients achieving a 32% reduction by week 4.

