#### **3 OBJECTIVES AND PURPOSE**

#### 3.1 PRIMARY OBJECTIVE

For patients with HPV+ squamous cancer of the oropharynx, fractionation of radiation will be individualized based on their PSI. Response will be measured after 20 days of RT as assessed by CT or MRI, as described in section 10.0. Primary objective is to increase the rate of response of  $\geq$  32% at 20 days to 63% of patients, above the expected 49%.

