4.2.1 On Treatment response at 4 weeks during RT

Week 4 CT and/or MRI will be loaded into the treatment planning system or other software for volumetric evaluation of tumor size. This will be compared against CT simulation or week 1 CT/CBCT and/or MRI, whichever is larger. The percent response will be calculated.

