# **10.2 DESCRIPTION OF STATISTICAL METHODS**

# 10.2.1 GENERAL APPROACH

This protocol is a single arm, phase II design with a primary endpoint of 63% of patients achieving  $a \ge 32\%$  reduction in tumor volume by week 4. This study will test the null hypothesis that the true response rate is equal to or less than a historical control of  $49\%^{11}$  versus the alternative hypothesis that it is greater than 49%.

Based on Fleming's 2-stage group sequential design, a total of 60 subjects will provide approximately 79% power with a type I error rate of 0.1 to detect a true response rate of 63%. The study will enroll subjects in two stages, with 49 subjects in the first stage. One interim efficacy/futility analysis will be conducted when the first 49 subjects have completed the study treatment and response evaluation. If the number of responsive patients is equal to or less than 27, the trial will be stopped for futility. If the number of responsive patients is equal to or greater than 30, the trial will be stopped for efficacy. Otherwise, the trial will continue to the second stage by enrolling 11 additional subjects.

At the final analysis with the total 60 subjects at the second stage, if there are equal to or more than 35 responsive patients, it will be concluded that the null hypothesis is rejected and the study treatment will be promising.

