# 10.2.3 ANALYSIS OF THE SECONDARY ENDPOINT(S)

- Assess complete response by CT at 2 months or PET/CT at 3 months following completion of therapy. This will be compared against historical controls.
- Response correlation with pre-treatment and during treatment radiomics features on PET/CT/MRI:

Radiomics features based on CT, MRI, PET-CT, noted during various imaging scans (pre-treatment, at 4 week of RT, and follow-up scan) will be correlated with the overall oncological response and outcome

Response correlation at 4 weeks and post treatment imaging with clearance of HPV from serum or oral gargle, and RSI/GARD.

 Correlate response and outcome to mathematical models of tumor growth and death dynamics pre-treatment and during treatment: Mathematical models will be generated based on the pattern of tumor growth and response as depicted by tumor volume measurement on various scans. These mathematical models will be validated by correlating with the overall response and oncological outcome

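### Where week-4 response is the outcome, the only methods named for the radiomics and mathematical-model correlations reduce it to responder or not, although percent volume change is calculated for each patient

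*Combined protocol and SAP*

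**What the plan says.** - **The measurement is continuous.** Section 4.2.1 loads the week-4 scan "for volumetric evaluation of tumor size", compares it with baseline, and adds: "The percent response will be calculated".
- **The definition of response is binary.** The Study Summary and Section 10.2.1 define week-4 response as a volume reduction of at least 32%. Section 2.3 gives the origin of the threshold: "Retrospective review of a Moffitt cohort (n=49) suggests that a cut point of 32% reduction".
- **The named methods need two groups or a binary outcome.** For radiomics, Section 10.1 correlates response "using two sample t-tests and univariate/multivariate logistic regression analysis as appropriate". For the models of tumour growth and death, the correlation "pre-treatment and during treatment will be performed using logistic regression analysis".
- **Some week-4 correlations have no method.** Section 10.2.3 lists "Response correlation at 4 weeks and post treatment imaging with clearance of HPV from serum or oral gargle, and RSI/GARD" and does not say how this will be done.
- **No continuous analysis of shrinkage appears anywhere.** The Pearson and Spearman coefficients in Section 10.2.5 compare HPV results between gargle and plasma only.

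**The concern.** A patient with 31% shrinkage and one with none are treated alike once volume change is cut at 32%, while patients at 31% and 33% are treated as opposites. The two-stage primary test needs a binary response because its boundaries count responders. A correlation with a radiomics feature or a model output does not.

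The mismatch is plainest for the mathematical models. Section 2.2 models tumour volume and reports the fit to individual response data as an r² of 0.98, and Section 10.2.3 builds the models from volumes measured on successive scans. Logistic regression on a 32% cut cannot show whether such a model predicts how much a tumour shrinks.

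The sample is small. There are at most 60 patients, and only 49 if the trial stops at stage 1. At stake is the power of the secondary objectives, not the primary conclusion.

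**Working it through.** **1. The plan's own design figure.** Section 10.2.1 states that "a total of 60 subjects will provide approximately 79% power with a type I error rate of 0.1". The rule is: stop for futility at 27 or fewer of 49, stop for efficacy at 30 or more, otherwise continue to 60 and require 35.

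P(success) = P(X₁ ≥ 30) + Σ over x = 28, 29 of P(X₁ = x) · P(X₂ ≥ 35 − x), with X₁ ~ Bin(49, p) and X₂ ~ Bin(11, p).

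- p = 0.63: 0.661 + 0.130 = 0.791. The stated power reproduces.
- p = 0.49: 0.058 + 0.035 = 0.093, within the stated 0.1.

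The trial continues only with 28 or 29 responders. That has probability 0.101 at p = 0.49 and 0.180 at p = 0.63, so it stops at 49 patients with probability 0.90 or 0.82. The plan states no power or precision for the secondary correlations.

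**2. Information kept by the split, under normality.** Inputs: the share of patients at or above the cut, 49% expected and 63% targeted (Section 3.1). The efficiency of a split normal variable relative to the continuous one is φ(z_p)² / [p(1 − p)].

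- p = 0.49: 0.3988² / 0.2499 = 0.1591 / 0.2499 = 0.636
- p = 0.63: 0.3776² / 0.2331 = 0.1426 / 0.2331 = 0.612

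Equivalent sample sizes: 60 × 0.636 = 38.2 and 60 × 0.612 = 36.7; 49 × 0.636 = 31.2 and 49 × 0.612 = 30.0. At 49% the cut sits near the median; at 63% it sits near the 37th percentile. The result barely differs.

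**3. Power under normality.** Simulation with n = 60, two-sided 5%, 4,000 data sets per setting: Pearson on the continuous change against a t-test by responder status. The correlations are illustrative.

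| True correlation | 49% above cut: continuous v split | 63% above cut: continuous v split |
|---|---|---|
| 0.30 | 65% v 45% | 66% v 44% |
| 0.35 | 79% v 58% | 79% v 59% |
| 0.40 | 89% v 73% | 90% v 70% |

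**4. Other error distributions.** Correlation 0.30, n = 60, 3,000 data sets per setting. Each cell gives the result with 49% / 63% above the cut. Efficiency is that of the split relative to Pearson.

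| Errors | Efficiency | Pearson % | Spearman % | Split % |
|---|---|---|---|---|
| Normal | 0.640 / 0.610 | 65.7 / 65.2 | 60.6 / 60.1 | 47.5 / 44.1 |
| Right skew | 0.698 / 0.833 | 65.3 / 65.0 | 67.4 / 68.2 | 49.9 / 56.4 |
| Left skew | 0.721 / 0.561 | 66.0 / 65.9 | 67.2 / 67.2 | 50.3 / 40.9 |
| t, 5 df | 0.879 / 0.835 | 68.6 / 68.2 | 71.5 / 71.5 | 60.9 / 57.9 |
| t, 3 df | 1.315 / 1.220 | 73.4 / 71.3 | 85.8 / 84.5 | 79.6 / 75.6 |
| Uniform | 0.365 / 0.392 | 65.7 / 64.8 | 57.8 / 57.3 | 29.7 / 32.0 |

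Spearman beats the split in all twelve settings; Pearson does not with 3 df.

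A harsher case marks the limit. With exponential errors, correlation 0.35 and 63% above the cut, the split had 94.9% power against 80.8% for Pearson. A further run of 3,000 data sets in that setting gave Spearman 93.5% and the split 94.5%, so there the rank analysis only about matches the split.

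**The case against.** **Which response is meant.** Section 10.1 says only response, and it leaves the choice of method open to what is appropriate. Section 10.2.3 relates radiomics and the models to overall response and oncological outcome. If that means complete response at 2 to 3 months (Section 4.2.2), the outcome is binary by definition, logistic regression is right and nothing is lost. This stands. A reader might infer that the plan expressly compares responders with non-responders at 32% in all its secondary correlations, but it never says so. What remains is conditional: for any of these correlations that uses week-4 response, no continuous method is named, and the latitude in Section 10.1 does not supply one.

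**HPV clearance and RSI/GARD.** A reader might count these among the analyses that lose power. The documents do not support that. These are the correlations that Section 10.2.3 ties explicitly to week 4, but no method is named for them, so the gap there is a missing specification.

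**The size of the loss.** About a third lost is one scenario. The documents give no distribution for volume change and no expected correlation, and the tables above show how far the figure moves. This also stands.

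**The cut has its own meaning.** Section 2.3 links it to locoregional control, and Sections 4.1 and 6.1 tie failure to reach it to a change of schedule in the conventional group. What predicts crossing 32% is therefore a fair question, which is a reason to keep the responder analysis as supportive. It is not a reason to make it the only one.

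**Nothing is irretrievable.** Percent change is recorded, so a continuous analysis could be added later. But it would then be chosen after the data are known.

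**Conclusion.** The point holds in a limited form. For radiomics and the mathematical models, Section 10.1 names only methods that use week-4 response as a yes/no variable, while the plan already produces the continuous measure.

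Under approximate normality the split keeps 61% to 64% of the information. Stopping at 49 patients is the likelier course at both design rates, so an equivalent sample of about 30 or 31 is as relevant as 37 or 38. The normality is an assumption. Under other shapes the loss can be larger (uniform), smaller (5 df) or absent relative to Pearson (3 df, exponential). The more robust result is that a rank correlation on the continuous change beat the split in every setting tabulated and about matched it in the one harsher case.

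The primary endpoint, its two-stage boundaries and the complete-response endpoint are unaffected.

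**What to change.** In Sections 10.1 and 10.2.3:

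1. State for each secondary correlation whether the outcome is week-4 response, complete response or a later outcome.
2. For the week-4 radiomics and mathematical-model correlations, make continuous volume change the outcome, as percent change or as the log ratio of week-4 to baseline volume. Analyse it by Spearman correlation or linear regression. Spearman gives the same answer for either scale, since one is a monotone function of the other, and it is the safer lead if the distribution is unknown.
3. Use the same outcome for the week-4 HPV-clearance and RSI/GARD correlations.
4. Keep the 32% responder analysis as the primary endpoint and as a supportive analysis here. Keep logistic regression for complete response.
5. State which volume is used (one lesion or the sum), since Section 4.1 contours each site separately. Give a floor value, or a rank analysis, for lesions with no contourable volume at week 4; a log ratio is undefined there.

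The cost is wording in a protocol amendment, which Section 13.2 sends to the IRB. No extra patients, scans or visits are needed.

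### Radiomics analyses include features from the scan that defines response, and test an unstated number of features in 49 to 60 patients without multiplicity control or internal validation

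*Combined protocol and SAP*

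**What the plan says.** Relating response and outcome to radiomics features is a secondary objective (section 3.2). Section 10.1 gives the method: response is related to pre-treatment and during-treatment features "using two sample t-tests and univariate/multivariate logistic regression analysis as appropriate". Section 10.2.3 adds the sources: "Radiomics features based on CT, MRI, PET-CT, noted during various imaging scans (pre-treatment, at 4 week of RT, and follow-up scan) will be correlated" with response and outcome.

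Response is itself read from those scans. Section 4.2.1 computes the on-treatment percent response from the tumour volume on the week-4 CT and/or MRI. Section 4.2.2 reads complete response from the 2-month CT or 3-month PET/CT, which is the follow-up scan.

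On sample size, section 10.2.1 states that "a total of 60 subjects will provide approximately 79% power with a type I error rate of 0.1", and "The study will enroll subjects in two stages, with 49 subjects in the first stage".

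The documents give no feature list or count, selection rule, multiplicity control, penalisation, cross-validation or validation set for radiomics. The validation mentioned in section 10.2.3 concerns the mathematical growth models, not the radiomics features.

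**The concern.** There are two distinct defects, and they need different remedies.

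**Circularity.** Neither section 10.1 nor section 10.2.3 pairs feature times with outcomes, so features can be tested against a response derived from the same scan. Sections 7.1 and 7.3 schedule protocol CT or MRI only at about day 1 and week 4 before treatment ends. The during-treatment features therefore come largely from the scan that defines week-4 response. Any feature that carries size or shape is then tied to response by construction.

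**Chance findings.** Many features tested one by one at a nominal level in 49 to 60 patients will give some significant results from noise. A multivariable model built on the best of them will look better in these patients than in new ones.

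At stake is the credibility of a stated secondary objective: a reader could not tell a radiomic signal from an artefact or from luck.

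**Working it through.** **1. The plan's own figure, and the likely sample.** Inputs from section 10.2.1: stop at 49 with 27 or fewer, or 30 or more, responders; reject at 60 with 35 or more; rates 49% and 63%. Exact binomial calculation gives power 0.791, which reproduces the stated figure of about 79%, and type I error 0.093, inside the 0.1 limit. The chance of stopping at 49 is:

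- true rate 63%: 0.661 (efficacy) + 0.159 (futility) = 0.82
- true rate 49%: 0.058 + 0.841 = 0.90

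So 49 is the likelier sample. At 60 patients and 63% response, non-responders number 60 × 0.37 ≈ 22.

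**2. Circularity.** Write V0 for baseline volume and V4 for week-4 volume. Response means V4/V0 ≤ 0.68. Since ln V4 = ln V0 + ln(V4/V0), any measure of V4 contains the quantity that is cut to define response.

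Simulation: 60 patients, 63% responding, V0 unrelated to response, 1,000 runs per setting. The standard deviations (SD) are assumptions. The table shows how often V4 is significant at 0.05 by t-test.

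| SD of ln V0 | SD of ln(V4/V0) = 0.2 | SD of ln(V4/V0) = 0.4 |
|---|---|---|
| 0.5 | 62.5% | 98.8% |
| 0.8 | 32.0% | 82.5% |
| 1.0 | 21.7% | 61.6% |

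Baseline volume was significant in 4 to 7% of runs, and change in volume in 100%. A stricter threshold does not help, because the association is real but built in.

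**3. Chance findings, single features.** The feature count m is an assumption. Expected false positives are 0.05m. If features are independent, the chance of at least one is 1 − 0.95^m.

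| m | Expected hits | Chance of at least one |
|---|---|---|
| 10 | 0.5 | 40% |
| 20 | 1 | 64% |
| 50 | 2.5 | 92% |
| 100 | 5 | 99.4% |
| 500 | 25 | about 100% |

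Correlation between features leaves the expected number of hits about the same but lowers the chance of any hit. At m = 100 with strong correlation (5 to 10 latent groups, within-group correlation 0.8 to 0.9, assumed) it is 58 to 85%.

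**4. Chance findings, multivariable model.** For illustration, the five features with the smallest p-values enter a logistic model. All features are noise. The table gives mean apparent AUC.

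| m | 60 patients, 33 responders, independent | Same, strongly correlated | 49 patients, 31 responders, independent |
|---|---|---|---|
| 50 | 0.81 | 0.69–0.74 | 0.85 |
| 100 | 0.85 | 0.69–0.74 | 0.88 |
| 500 | 0.90 | 0.70–0.76 | 0.93 |

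With 38 responders of 60 the independent figures are 0.82, 0.85 and 0.91. The true AUC is 0.50 throughout. With 100 features, selection inside 10-fold cross-validation returned 0.497.

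**5. Outcome events.** Section 2.3 reports 94.7% locoregional control at 3 years in comparable patients treated with radiation alone. Expected failures are 60 × 0.053 = 3.2, or 49 × 0.053 = 2.6.

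**The case against.** The strongest reply is that much of this pipeline is not in the plan. Section 10.1 names t-tests and logistic regression as appropriate to the data. It does not describe a screen, a five-feature rule, a significance level for radiomics, a prediction model or an AUC. A reader might infer that the plan prescribes screening followed by unpenalised modelling, so that noise is bound to look predictive. The documents do not support that. They leave the method open, and the AUC figures only show what an analysis within that freedom can produce. This part of the objection stands.

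The size of the chance-finding problem also depends on assumptions. The feature count is unknown, and features of one tumour are plausibly correlated. Correlation cuts the AUC excess over 0.50 by roughly a quarter to a half, but some excess remains.

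A reader might also picture a full grid of three modalities at every time point. Section 7.1 does not require pre-treatment PET/CT, and section 7.3 schedules no PET during treatment and allows CT or MRI. The grid will be smaller and incomplete.

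Finally, this is a correlative analysis, and no stopping rule, treatment assignment or primary conclusion depends on it. That limits the consequence. None of these replies touches the circularity or supplies the missing error control.

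**Conclusion.** The point holds as two separate defects in a secondary analysis, and should be corrected.

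Circularity follows from sections 4.2.1, 4.2.2 and 10.2.3 without any assumed feature count. Only its size depends on assumed variances: week-4 volume was significant in 22 to 99% of simulated trials in which baseline volume stayed near 5%. It does not extend to week-4 features tested against later outcomes.

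Chance findings are likely rather than certain. For an assumed 50 to 500 noise features, about 2.5 to 25 nominal hits are expected. Apparent AUC can reach about 0.81 to 0.90 under independence, or 0.69 to 0.76 under strong correlation, with 60 patients. Under independence the inflation is greater at 49.

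It would be wrong to infer any threat to the primary test or the sample size: the two-stage design reproduces its stated power and does not use radiomics.

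**What to change.** Amend sections 10.1 and 10.2.3 as follows.

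1. Do not test features against a response derived from the same scan. Use only pre-radiotherapy features for week-4 response, and only pre-radiotherapy and week-4 features for complete response. Change-from-baseline features that use the week-4 scan count as week-4 features.
2. Apply Benjamini-Hochberg false-discovery control across all features tested, and report how many were tested.
3. For any multivariable response model, use penalised logistic regression with selection inside cross-validation, or a bootstrap optimism correction that repeats the selection. Report the corrected performance.
4. Limit locoregional-failure analyses to descriptive summaries, since about 3 events are expected, and label all radiomics results hypothesis-generating.

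One limit remains: baseline volume is the denominator of percent response, so pre-radiotherapy size features keep some coupling to week-4 response and should be interpreted with that in mind.

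The cost is more analysis work, fewer features declared significant, and the loss of week-4 features as correlates of week-4 response. No extra patients, scans or visits are needed.
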